# **Abbreviations**

Abbreviation	Description
AE	Adverse Event
BAL	Bronchoalveolar Lavage
BPD	Bronchopulmonary Dysplasia
CI	Chief Investigator
CIG	Co-Investigator Group
СР	Cerebral Palsy
СРАР	Continuous Positive Airway Pressure
CRF	Case Report Form
CrUSS	Cranial Ultrasound Scan
DMC	Data Monitoring Committee
DSUR	Development Safety Update Report
GCP	Good Clinical Practice
HR	Hazard Ratio
IL	Interleukin
IMP	Investigational Medicinal Product
IRAS	Integrated Research Application System
IVH	Intraventricular Haemorrhage
MHRA	Medicines and Healthcare products Regulatory Agency
NEC	Necrotising Enterocolitis
NHS	National Health Service
NIHR	National Institute for Health Research
NPEU CTU	National Perinatal Epidemiology Unit Clinical Trials Unit
PDA	Patent Ductus Arteriosus
PEEP	Positive End Expiratory Pressure
PI	Principal Investigator
PIL	Parent Information Leaflet
PMA	Postmenstrual Age
PMG	Project Management Group
R&D	NHS Trust Research and Development Department
RCT	Randomised Controlled Trial
REC	Research Ethics Committee

RR	Risk ratio
SAE	Serious Adverse Event
SAR	Serious Adverse Reaction
SD	Standard deviation
SUSAR	Suspected Unexpected Serious Adverse Reaction
TNF	Tumour Necrosis Factor
TSC	Trial Steering Committee

#### **Trial Flow Diagram**

#### MINIDEX FLOW CHART

#### Eligibility criteria

- Born at <30 weeks' gestation
- Aged between 10 and 24 postnatal days (≥10 and ≤24)
- At high risk of developing BPD: receiving mechanical ventilation via endotracheal tube with at least 30% inspired oxygen when the PEEP is at least 4 cm water and, in the opinion of the treating physician, unlikely to be extubated within 48 hours
- · Receiving caffeine therapy
- Written informed parental consent
- Born to a mother aged 16 or over

#### **Exclusion criteria**

- Postnatal steroid treatment for prevention or treatment of respiratory disease
- No realistic prospect of survival
- Severe congenital anomaly affecting the lungs, heart or central nervous system
- Surgical abdominal procedure or PDA ligation
- Illness or medications for which postnatal corticosteroid would be contra-indicated
- Participation in another trial that would preclude baby from inclusion in Minidex

#### Randomised

Web-based randomisation (1:1 ratio) hosted by NPEU Clinical Trials Unit

#### **Active intervention**

Dexamethasone 50 mcg/kg/day for 10 days then alternate days for 6 days

# OR

#### Placebo control

0.9% saline same volume administered daily for 10 days then alternate days for 6 days

#### **Primary outcome**

Time to first extubation after first IMP dose (when the baby remains extubated for more than 24 hours)

### Secondary outcomes

- Time to first extubation after first IMP dose (whether or not more than 24 hours)
- Extubation by day 7\* (where the baby has remained extubated for more than 24 hours)
- Extubation by day 7\* (whether or not more than 24 hours)
- Survival to 36 weeks' PMA
- Markers of respiratory morbidity to 36 weeks' PMA (or discharge if sooner), as listed in protocol
- · Safety outcomes to 36 weeks' PMA (or sooner if discharged home), as listed in protocol
- · Parent/family experience

CTT01\_v13.0\_100922

#### **Exploratory outcome**

· Changes to the inflammatory cytokine profile (sampling sites only)

#### Tertiary outcomes

Metrics of feasibility: Recruitment, retention, adherence to protocol, ascertainment of outcomes

\*All references to 'day 7' within this protocol refer to 7 completed days from first IMP dose.

# **Study Summary**

CENEDAL INCODADATION								
GENERAL INFORMATION								
Short Title	Minidex							
Full Title	Minidex: The efficacy and safety of very low dose dexamethasone used to facilitate the extubation of ventilator dependent preterm babies who are at high risk of bronchopulmonary dysplasia.							
Sponsor	University of Liverpool							
Sponsor ID	UoL001206							
EudraCT No.	2015-005342-63							
REC Reference No.	16/NW/0396							
Chief Investigator	[name]							
Lead Clinician	[name]							
Co-ordinating Centre	National Perinatal Epidemiology Unit Clinical Trials Unit							
National / International	National							
TRIAL INFORMATION								
Phase	Randomised Phase 2b							
Indication	Prevention of bronchopulmonary dysplasia (BPD).							
Design	Multicentre, randomised, masked, parallel group, placebo controlled trial.							
Primary Objective	To determine if treatment with very low dose dexamethasone facilitates the extubation (for more than 24 hours) of ventilator dependent preterm babies of less than 30 weeks' gestation who are at high risk of developing BPD.							
Secondary Objectives	To determine if the treatment of ventilator dependent preterm babies of less than 30 weeks' gestation who are at high risk of developing BPD with very low dose dexamethasone impacts upon:							
	
 
Time to first extubation after first IMP dose (whether or not more than 24 hours)
 
Extubation (for more than 24 hours) by day 7
 
Extubation (whether or not more than 24 hours) by day 7
 
Survival to 36 weeks' postmenstrual age (PMA)
 
Respiratory morbidity to 36 weeks' PMA (or discharge home if sooner)
 
Safety outcomes
 
Parent/family experience
 
							
Exploratory Objective	To determine if the treatment of ventilator dependent preterm babies of less than 30 weeks' gestation who are at high risk of developing BPD with very low dose dexamethasone impacts upon cytokine profile.							
TRIAL TIMELINES								
Expected start date	01/11/2015							

Participant enrolment phase	01/09/2016 - 28/02/2018						
Follow-up duration	36 weeks' PMA						
•	Date of final data lock						
End of Trial Definition							
Expected completion date	30/10/2018						
TRIAL PARTICIPANT INFORMATIO	N						
Number of trial participants	94						
Number of trial sites	Up to 25						
Age group of trial participants	Preterm babies born less than 30 weeks' gestation and aged between 10 and 24 postnatal days.						
Inclusion criteria	
 
Born at <30 weeks' gestation
 
Aged between 10 and 24 postnatal days (≥10 and ≤24)
 
At high risk of developing BPD: receiving mechanical ventilation via endotracheal tube with at least 30% inspired oxygen when the positive end expiratory pressure (PEEP) is at least 4 cm water and, in the opinion of the treating physician, unlikely to be extubated within 48 hours
 
Receiving caffeine therapy
 
Written informed parental consent
 
Born to a mother aged 16 or over
 
						
Exclusion criteria	
 
Postnatal steroid treatment for prevention or treatment of respiratory disease
 
No realistic prospect of survival
 
Severe congenital anomaly affecting the lungs, heart or central nervous system
 
Surgical abdominal procedure or PDA ligation
 
Illness or medication for which postnatal corticosteroid would be contra-indicated (e.g. active fungal infection, confirmed or suspected acute sepsis, acute necrotising enterocolitis (NEC)/focal intestinal perforation or cyclooxygenase therapy)
 
Participation in another trial that would preclude baby from inclusion in Minidex
 
						
INVESTIGATIONAL MEDICINAL PR	ODUCT						
IMP name(s)	Dexamethasone Saline						
Duration of IMP Treatment	16 days 50 mcg/kg administered once daily for 10 days then alternate days for 6 days. Dose to be calculated on current working weight at trial entry; can be increased in line with current working weight as per local practice.						
IMP supplier	QP released from Guy's and St Thomas' (manufacturer)						
Non IMP name	Caffeine therapy						

#### 1. Introduction

# 1.1. Background

Bronchopulmonary dysplasia (BPD) affects approximately 35% of babies born at less than 30 weeks' gestation who survive to discharge from neonatal care. In the UK this equates to 1,450 affected babies a year. BPD prolongs hospitalisation and often requires home oxygen therapy for 6–12 months. It is associated with a significant long term respiratory and neurodevelopmental healthcare burden: each year up to 200 UK babies develop moderate/severe disability attributable to BPD. Therapies that reduce the burden of BPD will reduce the burden of neurodevelopmental and respiratory impairment that it entails. There are few interventions proven to reduce the incidence or severity of BPD.

Corticosteroids have been used in high dose regimens since the 1970s to reduce the impact of BPD. They have been shown in meta-analyses to facilitate the extubation of preterm babies and reduce the incidence of BPD at the expense of short-term metabolic and gastrointestinal side effects. A Cochrane review reported a risk ratio (RR), compared to placebo, for 'failure to extubate by the 7th day' of 0.64 (95% Confidence Interval (CI) 0.56 to 0.74) and a RR for 'reduction in the incidence of BPD' of 0.76 (95% CI 0.66 to 0.88). Facilitation of extubation and reduction of BPD is seen for both hydrocortisone and dexamethasone (at all published doses of dexamethasone, ranging from low (0.15 mg/kg/day) to high (0.6 mg/kg/day)) when administered at any postnatal age. Corticosteroid therapy became commonplace; in 1995, 72.5% of all surviving UK babies less than 26 weeks' gestation had received postnatal corticosteroids.

It is assumed that the effect of corticosteroids is mediated by amelioration of the lungs' inflammatory responses. BPD is known to be associated with elevated levels of proinflammatory cytokines  $^{10,11}$  and corticosteroid administration has been proven to reduce levels of these cytokines (e.g. interleukin (IL)-1 $\beta$ , IL-1ra, IL-6, IL-8 and tumour necrosis factor (TNF) $\alpha$ ) in affected babies. However, little is known about the cytokine:cytokine network interactions underpinning BPD, and the way in which these are modulated by corticosteroids has yet to be elucidated.

The risk-benefit balance of corticosteroids is complicated by its association with adverse neurodevelopmental outcomes. This was first reported in 1974 and in 2001 a meta-analysis reported that babies treated with high dose regimens of postnatal corticosteroids have an increased risk of long-term adverse neurodevelopmental outcomes (Cerebral Palsy (CP), RR 1.92 (95% CI 1.41 to 2.61)). However, further meta-analyses have shown that the risk of adverse neurodevelopmental outcomes is modified by both the postnatal age at which the corticosteroids are given and the baby's underlying risk of developing BPD. So the increased risk of adverse outcomes seen in the initial meta-analysis was attributable to those trials that included babies less than 7 days of age, treated to prevent BPD (CP RR 1.75 (95% CI 1.20 to 2.55)).6 The risk of CP is not increased in those trials treating babies over 7 days of age for evolving BPD (CP RR 1.06 (95% CI 0.76 to 1.5)) and the risk of the composite outcome of CP and death was reduced by corticosteroid administration in trials where the background risk of BPD exceeded 65%. Some clinicians advocate giving corticosteroids from birth in order to prevent BPD. Recent data suggests this approach may reduce the incidence of BPD7. However, many clinicians are concerned that giving corticosteroids to all babies born at extreme prematurity may expose many babies to corticosteroids unnecessarily. Accordingly, many clinicians use corticosteroids selectively, that is in babies more than 7 days old who are at high risk of developing BPD. Evidence about the efficacy of corticosteroids when administered to all premature neonates is not relevant to corticosteroids given 2 - 3 weeks after birth because responses to corticosteroids will change with time and doses given during the first

week will have effects on adaptation to extrauterine life that are not relevant if steroids are used selectively.

Some clinicians now use low or very low dose regimens to improve pulmonary function in babies at high risk of BPD after day 7 of life in the hope that, like other side effects, the effect on the brain is dose-dependent and low and very low dose regimens will avoid neurodevelopmental impairment while maintaining the beneficial pulmonary effects. There is insufficient evidence to support this. No low dose regimen starting after 7 days has been subjected to a randomised controlled trial adequately powered on neurodevelopmental outcomes. Such a trial is needed to inform clinical practice and this study is the necessary first step towards designing a large trial based on clinically meaningful outcomes.

In a retrospective cohort study we found that babies at risk of BPD who received a very low dose regimen were extubated significantly faster than controls who did not receive corticosteroids, hazard ratio (HR) 6.24 (95% CI 2.34 to 16.63). This regimen, Minidex (50 mcg/kg/day for 10 days then alternate days for 6 days) was derived from the physiological corticosteroid replacement dose, and is lower than the next lowest dose regimen that has been subjected to assessment of short-term outcomes (DART 150 mcg/kg/day with 10 day taper). Our cohort study suggested proof of concept for an effect of a very low dose of dexamethasone on short-term outcomes relevant to BPD. This now needs to be evaluated in a rigorously designed randomised controlled trial.

If the efficacy and acceptability of very low dose dexamethasone (Minidex) is established in this trial, the next step would be to conduct a large pragmatic multicentre randomised placebo controlled effectiveness trial examining substantive outcomes such as neurodevelopment at 2 years of age corrected for prematurity, building on the conduct and findings of this trial.

#### 1.2. Rationale for the Study

Systematic reviews indicate that there is a net benefit of giving postnatal corticosteroids to a group of selected preterm babies at high risk of BPD. However, there is a need to determine the optimal dose for postnatal corticosteroids. "High" doses are effective but may be associated with avoidable adverse effects. We will investigate a dosage regimen (Minidex) that is substantially lower than the lowest dose regimen that has been assessed to date. Proof of concept for the effect of Minidex on an appropriate surrogate outcome has been established in a retrospective cohort study. However, there is no definitive evidence of efficacy, size of effect or safety. Our long-term goal is to conduct an effectiveness trial aimed at establishing the 2-year neurodevelopmental outcomes of babies receiving Minidex.

Prior to the effectiveness trial we need to perform an efficacy study to determine short-term clinical efficacy and safety, acceptability to parents and clinicians and feasibility in terms of recruitment and retention. In this efficacy study, extubation and respiratory morbidity prior to hospital discharge are being employed as surrogate markers of pulmonary function. Collection of data regarding respiratory morbidity and the need for open-label medication to hospital discharge will increase our understanding of the biological processes and enable planning of the next step in evaluating this therapy.

This study offers an opportunity to gain a better insight into the inflammatory perturbations found in BPD as well as highlighting the mechanisms of action through which dexamethasone can influence the structure and interactions within inflammatory networks. Characterising key nodal (cytokine) perturbations within these networks among babies treated with dexamethasone or placebo may highlight novel potential targets for therapeutic intervention (i.e. the presence of hub/driver nodes),

or differences in inflammatory signatures between therapy responders versus non-responders. These results may indicate ways therapy could be targeted, avoiding unnecessary exposure in the future.

The aim of the study is to assess the efficacy and safety of very low dose dexamethasone used to facilitate the extubation of ventilator dependent preterm babies less than 30 weeks' gestation at high risk of developing BPD.

# 2. Trial Objectives

Objectives	Outcome Measures	Timepoint(s) of evaluation of this outcome measure (if applicable)						
Primary Objective								
To determine if treatment with very low dose dexamethasone facilitates the extubation (for more than 24 hours) of ventilator dependent preterm babies of less than 30 weeks' gestation who are at high risk of developing BPD.	Time to first extubation after first IMP dose when the baby remains extubated for more than 24 hours.							
Secondary Objectives								
To determine if the treatment of ventilator dependent preterm babies of less than 30 weeks' gestation who are at high risk of developing BPD with very low dose dexamethasone impacts upon:								
1. Time to first extubation (whether or not more than 24 hours)	Time to first extubation after first IMP dose (whether or not more than 24 hours)							
2. Extubation by day 7	

(a) Extubation by day 7 (where the baby has remained extubated for more than 24 hours)

(b) Extubation by day 7 (whether or not more than 24 hours)

	Day 7						
3. Survival to 36 weeks' postmenstrual age	Alive at 36 weeks' PMA (or discharge home if sooner)	36 weeks' PMA (or discharge home if sooner)						
4. Respiratory morbidity to 36 weeks' PMA	(a) Total duration of invasive ventilation	36 weeks' PMA (or discharge home if sooner)						

Objectives	r					
(or discharge home if sooner)	through endotracheal tube  (b) Total duration of non-invasive respiratory support through nasal CPAP, nasal ventilation or high flow oxygen therapy  (c) Open-label treatment using local unit policy i.e. escalation of corticosteroid therapy or requirement for repeated courses of corticosteroid.  (d) Use of diuretics using local unit policy  (e) Total duration of supplemental oxygen therapy  (f) Severity of BPD at 36 weeks' PMA (or discharge home if sooner) as defined in Appendix 1. Oxygen requirement will be determined using the oxygen reduction test (see Appendix 2).					
5. Safety outcomes	
 
a.) Hypertension
 
b.) Hyperglycaemia
 
c.) Confirmed/suspected sepsis
 
d.) Spontaneous gastrointestinal perforation or NEC (definitive and/or complicated (Bell stage II and above) confirmed by radiography and/or histopathology or requiring surgery)
 
e.) Deterioration in cranial ultrasound findings.
 
A new finding of severe IVH (grade III/IV with
 
	During administration of IMP and for 14 days after last dose of intervention (a-d)  CrUSS performed prior to randomisation (or when occurring according to standard clinical				

Objectives	Outcome Measures	Timepoint(s) of evaluation of this outcome measure (if applicable)
	bleeding) or new PVL on the CrUSS performed at 36 weeks' PMA (+/- 2 weeks) when compared to the scan performed most recently prior to randomisation  f.) Growth	practice) and at 36 weeks' PMA (+/- 2 weeks, or discharge home if sooner). Weight measured at trial entry, on day 14 (after randomisation) and 36 weeks' PMA (+/- 2 weeks, or discharge home if sooner)
	i) Change in standard deviation score (SDS) for weight between study entry and day 14 after randomisation.	
	ii) Change in standard deviation score (SDS) for weight between day 14 after randomisation and 36 weeks' PMA (or discharge home if sooner)	
	ii) Change in standard deviation score (SDS) for head circumference (as measured by occipito-frontal circumference) between study entry and 36 weeks' PMA (or discharge home if sooner)	Head circumference measured at trial entry, and at 36 weeks' PMA (+/- 2 weeks, or discharge home if sooner)
6. Parent/family experience	Parent/family experience: Measures of the parents'/family's hands on involvement in their baby's care.  (a) Duration, frequency and amount of contact with their baby  (b) Degree of parental/family involvement in cares (nappy changes, skin care, etc.)	Log recorded during 16-day intervention period. Although part of the consent process, this is not part of the source dataset and is optional for parents and staff to complete

Objectives	Outcome Measures	Timepoint(s) of evaluation of this outcome measure (if applicable)					
Exploratory Objective							
Cytokine profile	Changes to the inflammatory cytokine profile	Endotracheal tube secretions and blood					
(Consenting babies from specified sites only)	in blood and endotracheal tube secretion fluid (a mechanistic marker of response)	samples taken at trial entry, and on days 4, 7, 10, 14 of the IMP administration schedule					
Tertiary Objectives							
To assess the acceptability and feasibility of the trial in order to inform the design of the subsequent effectiveness trial by reporting metrics related to:							
1. Recruitment	Recruitment rate	Trial completion					
2. Retention	Retention rate	Trial completion					
3. Adherence to protocol	Use of open-label therapy and completion of course	Trial completion					
4. Completeness of data	Ascertainment of outcomes	Trial completion					

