#### 7. Statistical Considerations

#### 7.1. Sample Size / Power Calculations

For the primary outcome of time to extubation, assuming 90% power and two-sided 5% level of significance, a log rank test with a sample size of 70 babies (35 in each arm) would be required to detect a HR of 2.3 when the control group hazard rate is 1.0. This HR is the lower end of the confidence interval found by our retrospective study; adjusted HR 6.24 (95% CI 2.34 to 16.63). This sample size will allow the detection of a clinically important absolute risk reduction of 36% for the secondary outcome of failure to extubate by day 7, with 90% power, a two-sided 5% level of statistical significance, and a control group incidence of 80%, (consistent with control group event rates reported in previous trials). As other previously published randomised trials of dexamethasone report failure to extubate by day 7 as a primary outcome, we consider this an important secondary outcome to consider in the sample size calculations.

Since all centres routinely collect the required data we anticipate a negligible loss to follow-up. However, as the primary analysis will be per-protocol, babies will be censored for the primary outcome (and other time-to-event outcomes) if the baby either dies, discontinues treatment before extubation, or remains intubated at day 16 (last day of the intervention period). These babies will be excluded from the analysis of other secondary outcomes.

Studies and published data sets show that 13.5–18% of babies <30 weeks' gestational age will have late onset sepsis, 2,18 7% will be treated for NEC,1 and 14% will be treated for PDA with cyclooxygenase inhibitors. We estimate that a third of late onset sepsis, half of NEC and a quarter of treated PDA would occur in the study period. We therefore expect that up to 14% of babies will permanently discontinue the study treatment for clinical reasons. We estimate that 10% of babies will either die before extubation, or remain intubated at day 16. These deaths will be reported to the DMC who will monitor for any safety imbalances or differences in censoring rates between the groups. The per-protocol analysis will therefore censor or exclude approximately 23% of all babies giving a final overall sample size target of at least 90 babies.

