### 7.3. Statistical Analysis

Demographic factors, clinical characteristics, and service utilisation will be summarised with counts (percentages) for categorical variables, mean (standard deviation (SD)) for normal distributed variables or median (interquartile or other percentile range) for other continuous variables.

Comparative statistical analysis will entail calculating the HR plus 95% confidence interval (CI) for the primary outcome, the risk ratio (plus 95% CI) for dichotomous outcomes, and mean or median difference (plus 95% CI), for other continuous variables. Since this is an efficacy study, for the primary analysis, babies will be analysed on a per-protocol basis, excluding babies who are discontinued from the study treatment. For the primary outcome events will be censored for babies who discontinue or die before extubation or who remain intubated at day 16.

A secondary analysis will analyse all outcomes on an intention-to-treat basis. The consistency of the effect of dexamethasone will be explored to see whether it is of particular help to specific subgroups of babies, using the statistical test of interaction. The following pre-specified subgroups will be examined for the primary outcome (1) gestational age, (2) singleton vs. multiple pregnancy and (3) diuretic use at trial outset.

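### Raw total durations of respiratory support are cut short by deaths that stay in the analysis, and non-invasive support can lengthen when extubation comes earlier

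*Protocol*

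**What the plan says.** Protocol Section 2, secondary objective 4, lists three durations followed to 36 weeks' PMA or earlier discharge home: (a) "Total duration of invasive ventilation", (b) "Total duration of non-invasive respiratory support through nasal CPAP, nasal ventilation or high flow oxygen therapy" and (e) "Total duration of supplemental oxygen therapy". Item (f) is "Severity of BPD at 36 weeks' PMA (or discharge home if sooner) as defined in Appendix 1". Survival is a separate outcome (objective 3).

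Section 7.3 gives the comparison: "mean or median difference (plus 95% CI), for other continuous variables". In the primary analysis "babies will be analysed on a per-protocol basis, excluding babies who are discontinued from the study treatment"; a secondary analysis takes every outcome by intention to treat.

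Section 7.1 goes further on exclusions. It censors a baby for time-to-event outcomes "if the baby either dies, discontinues treatment before extubation, or remains intubated at day 16", and leaves the same babies out of the other secondary outcomes. The protocol does not say how a death enters a duration.

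**The concern.** A total duration is a sound measure of morbidity only if every baby could accumulate days over the same window. A baby who dies stops accumulating, and a low total then reads as little morbidity. If deaths differ between arms, the arm with more of them gains on the durations.

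Outcome (b) has a second problem that needs no deaths. The trial tests whether the drug brings extubation forward. A baby extubated sooner may spend the days gained on CPAP, nasal ventilation or high flow, and (b) counts those days as morbidity. The drug working as intended could then appear as a worse result.

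BPD severity has a related gap. Appendix 1 grades oxygen and support need at 36 weeks' PMA, so a baby who has died has no grade, and no listed outcome joins BPD with death.

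Section 1.2 uses respiratory morbidity as a surrogate for pulmonary function and expects it to help plan the next trial, so a wrong direction here would carry forward.

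**Working it through.** The protocol gives no durations, SDs or death rates by arm, so there is no plan figure on this point to reproduce. What follows shows direction and an order of size under stated assumptions.

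**1. Death and a mean total, by hand.** Assume survivors average 30 ventilated days and deaths fall near day 5. The shift in the arm mean is (30 − 5) × excess deaths:
- 5 points: 25 × 0.05 = 1.25 days shorter
- 10 points: 25 × 0.10 = 2.5 days shorter

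**2. Inputs for a simulation (200,000 babies per arm).**
- From Section 7.1: hazard ratio 2.3, and 80% of controls not extubated by day 7. If times are exponential, the rate is −ln(0.80)/7 = 0.0319 per day and the median ln 2/0.0319 = 21.7 days.
- Assumed: control median 14 or 21.7 days; one extubation per baby, no re-intubation; median 30 days of non-invasive support after extubation, the same in both arms; deaths uniform over days 1 to 28; window 56 days (42 and 70 also tried with the 21.7-day median). Oxygen was not simulated.

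**3. Differences in mean days** (arm with more deaths, or treated arm, minus the other):

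| Scenario | Analysis | (a) invasive | (b) non-invasive | (a)+(b) |
|---|---|---|---|---|
| No drug effect, deaths 20% v 10% | Intention to treat | −1.0 to −1.8 | −1.0 to −2.1 | −2.2 to −3.9 |
| Same | Per-protocol, Section 7.1 exclusions | about −0.1 | −1.2 to −2.1 | – |
| HR 2.3, equal deaths (0% or 10%) | Intention to treat | −9.4 to −14.5 | +4.7 to +7.0 | −3.2 to −8.1 |
| Same | Per-protocol, Section 7.1 exclusions | −0.8 to −1.3 | +0.1 to +0.5 | – |

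- Row 1: death alone looks like benefit. Medians are not immune: they shift by 0.9 to 2.0 days for (a) and 1.7 to 3.2 days for (b).
- Row 2: in the per-protocol set the shortening falls on (b). In this model a baby who dies after extubation has already completed (a). About 30% to 70% of babies who die are extubated by day 16 before death and so stay in.
- Row 3: a working drug lengthens (b), although total support (a)+(b) is shorter.
- Row 4: the differences nearly vanish because the exclusions remove the longest-ventilated babies unequally. With the 21.7-day median and no deaths, those still intubated at day 16 are exp(−0.0319 × 16) = 60% of controls and exp(−2.3 × 0.0319 × 16) = 31% of treated babies. Over all settings the exclusions are 45% to 61% against 16% to 32%.

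**4. Does the proposed measure point the right way?** Days alive and free of any support = window − support days − days dead. The mean day of death is 14.5. For deaths 20% v 10% over 56 days, extra days dead are 0.10 × (56 − 14.5) = 4.15 and support days are fewer by 2.92 to 3.16. The net is 0.99 to 1.23 fewer days alive and free. Over 42 days it is 2.75 − 2.23 = 0.52 fewer, and over 70 days 5.55 − 3.89 = 1.66 fewer. The arm with more deaths now does worse. With HR 2.3 and equal deaths, the treated arm gains 3.2 to 8.1 days.

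**The case against.** A reader might infer that early death counts as a short duration throughout the trial, including its primary analysis. The protocol does not support that. The primary analysis is per-protocol, and Section 7.1 removes babies who die before extubation from these outcomes. A ventilated baby who dies on day 5 contributes nothing there. The difficulty in that analysis is a different one, selection on a post-randomisation event, and Sections 7.1 and 7.3 do not describe the excluded babies identically.

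Other points carry weight:
- A mean or median difference is a generic effect measure. An analysis plan, not shown here, could restrict durations to survivors without contradicting the protocol. That tempers the point about deaths. It does not alter the definition of (b), which the protocol fixes.
- Survival is reported separately and the DMC watches for imbalance, so unequal deaths would be visible. With equal deaths there is little or no bias from this source.
- Outcomes (a) and (b) are listed together, so a careful reader can see days move between them. That aids interpretation but does not let (b) be read alone.
- Section 7.1 expects 10% of babies to die before extubation or remain intubated at day 16, combined. A 10-point excess of early deaths is extreme against that, and the exponential exclusion rates above far exceed it.
- With 47 babies per arm and an assumed SD of 10 to 15 days, the 95% half-width is 1.96 × SD × √(2/47), about 4 to 6 days. A 1 to 2.5 day bias lies within the noise.
- BPD at 36 weeks' PMA can only be graded in survivors. That is no error in itself; the gap is the absence of a companion outcome that includes death.

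**Conclusion.** The point holds in limited form. Death shortens the raw totals in the intention-to-treat analysis and, for babies who die after extubation, in the per-protocol analysis, where the model puts nearly all of the effect on (b). It biases the comparison only if deaths differ between arms. The size, about 1 to 2.5 days for a 5 to 10 point excess, rests on assumed durations.

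The firmer part is outcome (b), which has no clear direction of benefit even with equal deaths. The lengthening of about 5 to 7 days assumes that need for non-invasive support after extubation does not itself shrink with treatment. If it did, the lengthening would be smaller or could reverse, and (b) alone could not tell these cases apart.

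These are secondary outcomes. The primary outcome, sample size and power are untouched. This is a cheap improvement to outcome definitions, not a fault that invalidates the trial.

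**What to change.** - Keep (a), (b) and (e) as descriptive totals, reported in survivors, with (a) and (b) presented and read together.
- Add, in the intention-to-treat analysis, days alive and free of invasive ventilation, of any respiratory support, and of supplemental oxygen. Count from randomisation (or from first dose among dosed babies) over a window closing at 36 weeks' PMA for every baby. Count days after death as not free, and state how days after discharge before 36 weeks are handled.
- Add death or moderate/severe BPD at 36 weeks' PMA beside BPD severity in survivors.
- Make Sections 7.1 and 7.3 agree on which babies the per-protocol analysis of these outcomes leaves out.

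The cost is wording in the outcome table and the analysis plan; the new measures come mainly from data already collected. The downside is that they mix mortality with morbidity, and counting days after death as not free is a value judgement. Deaths, support days in survivors and BPD in survivors must therefore be shown alongside.
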